Sigh breaths may improve CO_2 clearance,⁽¹³⁾ oxygenation and lung mechanics^(14, 16) in neonate. Currently, only 4 studies in HFOV-sigh mode were conducted. The first and second studies were registered in Clinical trial.gov.^(17, 18) Preterm (gestational age 24–36 weeks) neonates were enrolled to crossover RCT between HFV and HFV-sigh groups to compare oxygenation and lung volume in both periods. The sigh peak inspiratory pressure (PIP) was set at 30 cm H₂O. Both trials have still been active studies and outcome data not reported in the clinicaltrial.gov. The third study in Japan was a practical advice in preterm (especially for infants born at less than 28-week gestation). They applied sigh breaths (2-3 times per minute, 0.7-1.0 seconds in duration) with sigh PIP at 5 cm H₂O above the current mean airway pressure (MAP).⁽²¹⁾ The final study compared HFJV with or without sigh breath in neonate with respiratory distress syndrome (RDS) and meconium aspiration syndrome (MAS).⁽²²⁾

We hypothesized that sigh breaths augment restoring lung volume and ventilation in intubated neonate with HFOV. In neonatal studies, the results from HFOV combined with intermittent sigh breaths have never reported (active 2 studies and review 1 study).^(17, 18, 21) This study, therefore, was designed to examine the short-term effects of sigh breaths during HFOV in neonate undergoing mechanical ventilation.

Methods

Study design: before-after interventional, non-randomized trial, study

Study setting: Neonatal Intensive Care Unit (NICU), Songklanagarind Hospital

Target population: NICU admitted neonate

Study population: Intubated neonate

Inclusion criteria:

- Preterm and term neonate (gestational age 24-41 weeks) with postnatal age less than 28 days
- Already ventilated with high frequency ventilation at least 1 hours
- An umbilical or peripheral arterial catheterization was available

Exclusion criteria

- Previous or current pulmonary air leaks (pulmonary interstitial emphysema, pneumothorax, pneumomediastinum, and pneumopericardium)
- Heterogeneous lung disease including MAS, congenital diaphragmatic hernia
- Suspected lung hypoplasia
- Suspected or confirmed intraventricular hemorrhage grade III-IV
- Suspected or confirmed hypoxic ischemic encephalopathy or 5-min Apgar score less than 3
- Hemodynamic instability despite using inotrope(s)
- Arterial pCO₂ level less than 45 mm Hg or more than 70 mm Hg before intervention

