- Neonates who were ventilated with HFOV would be informed consent to the parents by the neonatal fellow ([name]). After informed consent, the first arterial blood gas was drawn after on HFOV at least 1 hour. Then, participants would be switched on HFOV-sigh mode (the same setting of HFOV mode and add only sigh breath). The second arterial blood gas was drawn (2 hours to 2 hours 15 minutes after start HFOV-sigh). After that sigh breaths would be switched off then on only HFOV mode.
- The ventilator in NICU had 4 brands (SLE6000, Drager, Fabian, and Sensor medic); however, sigh mode was only available in SLE6000 infant ventilators (United Kingdom) and Drager Babylog VN500 (Germany).
- HFOV-sigh setting both SLE6000 and Drager Babylog VN500: setting (Hz, MAP, delta pressure) same as HFOV, set sigh RR 3 breath/min, Sigh Ti = 1 sec, Sigh PIP = (MAP+5, maximum 30) cm

 H_2O , Slope sigh 0.5. No change in Hz, MAP, delta pressure, and increased FiO_2 less than 0.1 occurred between intervention.

Currently, only 3 studies in HFOV-sigh mode were conducted (Table 1). We set sigh RR 3 breath/min and Sigh Ti = 1 sec (similar to previous studies^(17, 18, 21)), Sigh PIP = (MAP+5,⁽²¹⁾ maximum 30^(17, 18)) cm H₂O. While HFJV combined with higher sigh PIP (set at 27 and 37 cm H₂O in RDS and MAS) resulted in excessive tidal volume.⁽²²⁾

| Author | Population | Mode of | Si | Sigh | | |
|-----------------------------|---------------------|------------|-----------------------|---------|---------|----------|
| | | ventilator | Sigh PIP | Sigh RR | Sigh Ti | Duration |
| | | | (cm H ₂ O) | (/min) | (sec.) | |
| Heiring ^(17, 18) | Preterm neonate | HFOV | 30 | 3 | 1 | 1 h |
| Nakanishi ⁽²¹⁾ | Preterm neonate | HFOV+VG | MAP+5 | 2-3 | 0.7-1.0 | N/A |
| Romo ⁽²²⁾ | Preterm and Term | HFJV | 27 (RDS) | 6 | 0.3-0.4 | N/A |
| | neonates | | 37 (MAS) | | | |
| Bonacina ⁽¹⁴⁾ | Neonate and infant | PSV | 30 | 1 | 3 | 240 |
| | | | | | | breaths |
| Nacoti (13) | Children undergoing | PSV | 30 | 1 | 0.5 | 1 h |
| | major surgery | | | | | |
| Mauri ⁽¹⁰⁾ | Adult with ARDS | PSV | 35 | 2,1,0.5 | N/A | 20 min |
| Mauri ⁽¹⁵⁾ | Adult with ARDS | PSV | 30 | 1 | N/A | 30 min |
| Badet ⁽²³⁾ | Adult with ARDS | A/C | <40, 2*TV | 2-3 | N/A | 1 h |

Table 1. Review sigh breaths in neonates, children, and adults with HFOV

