A/C= assist controlled, HFJV = high-frequency jet ventilation; HFOV = High frequency oscillatory ventilation; VG = Volume guarantee; MAP = Mean airway pressure, MAS = Meconium aspiration syndrome; N/A = not available; PIP = peak inspiratory pressure; PSV = pressure support ventilation; RDS = Respiratory distress syndrome; RR = Respiratory rate; Ti = Inspiratory time; TV = tidal volume

• The monitoring during HFOV and HFOV-sigh monitoring was vital signs (systolic, diastolic, mean arterial pressure, heart rate, SpO₂ were collected every 15 minutes during intervention for 2 h and after intervention for 1 h) by neonatal fellow ([name]) and nurse, clinical manifestations, respiratory distress, umbilical arterial blood gas during study, and chest X-ray within 24 hours after intervention or immediately if clinical conditions deteriorate. The first blood gas was obtained after HFOV mode at least 1 hour with stable participants. After HFOV-sigh, the blood gas was obtained after 2 hours (no more than 2 hours 15 minutes) in this setting.

Data collection

Participant's data and blood gas's result will be recorded in record form.

Data management

EpiData entry is used for data entry and data documentation. The data will be safe and private collected; moreover, only principal investigator and recorder will access.

Data analysis

Parametric continuous variables are presented as mean (standard deviation, SD) and paired t-test was used to compare paired samples. Nonparametric continuous variables are presented as median (interquartile range, IQR) and the Wilcoxon signed rank test with continuity correction was used to compare paired samples. Subgroup analysis for gestational age less than 37 and 32 weeks.

Ethical issues

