For Safety, the intermittent sigh breaths generated low sigh RR, optimal sigh PIP and Ti from previous studies. For 2 hours, neonatal fellow will monitor clinical conditions and then 24 hours after intervention. Risk of sigh breath may be air leak syndrome because this mode may increase PIP sigh and ventilation. In metaanalysis in neonate, neonates who on HFOV mode developed pulmonary air leaks 27.7% (392/1,415).⁽¹⁾ However, neonate with risk of air leak syndrome (previous or current pulmonary air leaks e.g., pulmonary interstitial emphysema, pneumothorax, pneumomediastinum, and pneumopericardium. Heterogeneous lung disease including MAS, congenital diaphragmatic hernia, and suspected lung hypoplasia) will be excluded and the participants will be closed-monitored during and 24 hours after intervention (clinical and radiographic conditions). Some neonates may expose X-ray (increase 1 time) more than routine care to monitor safety. However, some neonate may need follow X-ray by clinical condition of each neonate within 24 hours, this neonate will not be repeat more X-ray.

The blood gases were drawn for 2 times, more than routine care. The arterial blood gases were only drawn through umbilical or peripheral arterial catheter for reducing pain from direct artery puncture. Each time used approximately 0.2 mL of blood (Total blood 0.4 mL). Arterial blood gases were needed to evaluate patient's ventilation. In case of lowest birth weight 500 g neonate, total blood loss was about 0.8 mL/kg/day (< 2.5 mL/kg). The methods of arterial blood gas drawing were firstly the doctor would draw blood containing heparin from umbilical artery catheter to the first syringe by sterile technique then the tuberculin syringe was secondly drawing from umbilical artery catheter to be analyzed for arterial blood gas. Thirdly, the blood from the first syringe was returned to the patient and finally the blood was clear from umbilical or peripheral arterial catheter by 0.5 mL flushing with normal saline. The maximum allowable blood draw volumes were shown in **Figure 6**.

| Maximum allowable blood draw volumes: | | | | | | |
|---------------------------------------|-----|--------------|---------------------------------|----------------------------------|--|--|
| PATIENT'S WEIGHT | | TOTAL VOLUME | MAXIMUM mL IN ONE BLOOD DRAW | MAXIMUM mL IN A 30-DAY PERIOD | | |
| Kg | lbs | mL | 2.5% of total blood vol | 5% of total blood vol | | |
| 1 | 2.2 | 100 | 2.5 | 5 | | |

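### The baseline gas needs only 1 hour of HFOV and an undefined stability, so pCO2 still moving from HFOV start or a recent settings change is counted as sigh effect

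*Combined protocol and SAP*

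**What the plan says.** The Methods section declares the design openly: "Study design: before-after interventional, non-randomized trial, study". There is no control group and no HFOV-only control period.

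Three places govern the baseline:

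- Inclusion criteria: "Already ventilated with high frequency ventilation at least 1 hours".
- Procedure, first bullet: "the first arterial blood gas was drawn after on HFOV at least 1 hour".
- Procedure, monitoring bullet: "The first blood gas was obtained after HFOV mode at least 1 hour with stable participants".

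The word stable is not defined. It describes the participants and does not mention ventilator settings or a repeat gas.

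The fixed-settings condition is in the HFOV-sigh setting bullet of the Procedure: "No change in Hz, MAP, delta pressure", together with a limit on the rise in FiO2. It applies to the interval of the intervention. No corresponding condition covers the time before the first gas.

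The follow-up gas has a tight window: "The second arterial blood gas was drawn (2 hours to 2 hours 15 minutes after start HFOV-sigh". The step from first gas to sigh start is given as a sequence with no time limit.

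The Ethical issues section confirms two study gases: "The blood gases were drawn for 2 times, more than routine care". After the second, "After that sigh breaths would be switched off then on only HFOV mode", and no further gas is planned. Data analysis compares before with after by paired t-test or Wilcoxon signed rank test, with no allowance for trend.

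**The concern.** HFOV itself changes pCO2, and the Background says that adjusting amplitude, frequency and mean airway pressure modulates ventilation. An infant just over 1 hour into HFOV, or one whose settings were recently adjusted, can supply a valid baseline if judged stable. If pCO2 has not levelled off by then, it keeps moving during the next 2 hours, while sighs are running. The paired test cannot separate that movement from the sigh effect, because every infant receives HFOV first and HFOV-sigh second.

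The planned difference is small, 1.9 mm Hg, so a modest background trend matters. A downward trend could produce a significant result with no sigh effect, and an upward one could hide a real effect. The Sample size section also allows the study to stop after a preliminary analysis if the difference is significant, so a result driven by drift could end recruitment early.

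This is a separate matter from regression to the mean. A second qualifying gas would deal with infants selected on a chance-high value, but it would not settle a pCO2 that is truly still changing.

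**Working it through.** **Inputs from the Sample size section:** difference 1.9 mm Hg, SD 4.35 mm Hg, alpha 0.05, power 80%, 42 infants, raised to 50. Sidedness is not stated; two-sided is assumed.

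**The plan's own figure.** n = (SD × (z0.975 + z0.80) / difference)² = (4.35 × 2.8016 / 1.9)² = 41.14, rounded up to 42. This reproduces the plan. A one-sided test would give 33, so two-sided is the reading that fits. 42 × 1.2 = 50.4, stated as 50.

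**Smallest significant mean change at n = 50.** t(0.975, 49 df) × SD / √n = 2.010 × 4.35 / √50 = 2.010 × 0.615 = 1.24 mm Hg. Over 2 hours that is about 0.6 mm Hg per hour.

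**Drift with no sigh effect.** Let D be the mean background fall over the 2 hours. The paired t statistic is noncentral t with 49 df and noncentrality D × √50 / SD. D is an assumption throughout, because the documents give no figure for it. The chance of two-sided p<0.05 is:

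| Mean fall, all 50 infants (mm Hg) | SD 4.35: noncentrality | SD 4.35: chance | SD 6: chance |
|---|---|---|---|
| 0 | 0 | 5% | 5% |
| 0.5 | 0.81 | 12.5% | 8.9% |
| 1.0 | 1.63 | 35.7% | 21.1% |
| 1.5 | 2.44 | 66.7% | 41.0% |

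SD 6 is included because 4.35 is the average of the two single-condition SDs, (3.7 + 5.0)/2, and not an observed SD of paired changes. With zero correlation between the gases, the SD of the change would be √(3.7² + 5.0²) = 6.2.

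**Drift in only some infants.** Suppose 20% fall by d and the rest do not drift. The mean fall is 0.2d and the variance becomes 4.35² + 0.2 × 0.8 × d².

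| d (mm Hg) | Mean fall | SD | Chance of p<0.05 |
|---|---|---|---|
| 1.0 | 0.2 | 4.37 | 6% |
| 1.5 | 0.3 | 4.39 | 8% |
| 2.0 | 0.4 | 4.42 | 10% |

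**Drift in the other direction.** With a true sigh effect of 1.9 mm Hg and no drift, power at n = 50 is 86%. An upward drift of 1.0 mm Hg leaves a net fall of 0.9 and cuts power to 30%.

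**The case against.** The case on the other side has several sound parts.

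- **The sign of drift is unknown.** A reader might infer that drift must favour the hypothesis, since infants enter with pCO2 of 45 to 70 mm Hg and may have just been adjusted to lower it. The documents do not say so. That range is an eligibility window and is nowhere described as a trigger for changing settings. This stands: the bias may go either way.
- **Many infants may be well settled.** One hour is a minimum. Under Informed consent process, parents are approached within a few days of intubation and given a 30 to 60 minute explanation, and consent precedes the first gas. The larger percentages require a mean drift over all 50 infants. This also stands, and it is why the 20% scenario is shown beside them.
- **Stability is mentioned, and the withdrawal rule may reach further back.** Under Subject withdrawal criteria, worsening with changed settings leads to withdrawal during the study, a wider phrase than the one used in neighbouring criteria. It could cover the time from consent to the first gas. Even so, it concerns infants who worsen, and it sets no minimum time on unchanged settings.
- **The sequence implies that sighs start promptly.** That is the natural reading, so the missing limit is a minor part of the point.
- **The record form is not shown.** It cannot be said that the elapsed times go unrecorded, only that the protocol text does not ask for them.

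What remains is that a plan followed exactly as written can take a baseline from an infant whose pCO2 is still responding to HFOV or to a recent change.

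**Conclusion.** The point holds as a gap in how the baseline is defined, within a before-after design that the protocol declares. The fixed-settings condition protects the 2 hours between the gases but not the run-up to the first one, and the analysis takes the whole change as the effect.

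The size depends on assumptions that the documents cannot settle. With no sigh effect, n = 50 and SD 4.35, the chance of p<0.05 runs from about 6% to 10% if a fifth of infants fall by 1.0 to 2.0 mm Hg. It is 13% to 67% if the mean fall across all infants is 0.5 to 1.5 mm Hg. A reader might take the upper figures as the trial's expected false-positive rate, but nothing in the documents supports a drift of that average size. Nor do they show that drift occurs at all; they show only that the plan does not guard against it.

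The sample-size arithmetic is not in question here. The issue is attribution, and it merits a change because the remedy is cheap.

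**What to change.** 1. For the study baseline, require that frequency, mean airway pressure and delta pressure have been unchanged for a stated time, at least 1 hour, before the first gas. Count that time after the first hour on HFOV. Otherwise an infant started exactly 1 hour earlier on untouched settings would qualify at once. If care changes the settings, the first gas is simply taken later; the condition governs study timing and does not direct ventilator management.
2. Start sighs within 15 minutes after the first gas, matching the tolerance already set for the second.
3. Record, at the first gas, hours since HFOV start and hours since the last settings change. Pre-specify a supportive analysis of the paired change by these times, with a stated cut-off for settled infants, reported beside the primary paired test.
4. State in the report that the before-after change cannot be attributed to sighs alone. The steps above reduce drift; none supplies a comparison without sighs over the same 2 hours.

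The cost is a few lines in the Procedure, two time fields (if the record form lacks them) and one supportive analysis. Some first gases will come later and a few infants may be missed. No extra blood sample is needed and the target of 50 is unchanged.

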Previous physiologic studies in intubated adults, sigh may improve lung function through improved lung elastance (increased gas exchange and lung volume, and decreased the respiratory drive)⁽⁹⁾ and enhance regional lung protection (decreased regional lung strain and intra-tidal ventilation heterogeneity).⁽¹⁰⁾ In an animal study, large inflations or sighs increased release of active surfactant.⁽¹¹⁾

In intubated animal study, rat took a spontaneously deep (sigh) breath which resulted in a rapid fall of pCO₂ (from 30 to 26 mm Hg).⁽¹²⁾ In intubated pediatric patients after major surgery, arterial pCO₂

decreased from pressure support ventilation (PSV, 39.3 ± 3.3 mm Hg) to "PSV + sigh" group (34.3 ± 4.6 mm Hg; p <0.001)⁽¹³⁾ while arterial pCO₂ was not significantly different in neonatal patients (PSV vs. PSV + sigh, mean \pm SD 42.3 \pm 3.7 vs 40.4 \pm 5)⁽¹⁴⁾ and adult patients (PSV vs. PSV + sigh, median [interquartile ranges] 44 [38, 49] vs. 43 [39, 47] mm Hg, p = 0.70).⁽¹⁵⁾

Besides pCO_2 level, sigh breaths improved oxygenation and lung mechanics in neonate. In crossover randomized controlled trial (RCT) from 11 neonates (median age 11.5 [8.7–74] days) after cardiac surgery, PSV + sigh mode significantly increased PaO_2/FiO_2 , inspiratory time and tidal volumes, and decreased oxygenation index and respiratory rate compared to PS mode.⁽¹⁴⁾ In 48 healthy preterm infants (weight at study 2,042 ± 316 g and postconceptional age 36.6 ± 2.0 weeks), mean ± SD. functional residual capacity (FRC) after sigh breaths, after apneic pauses, and neither a sigh nor an apneic pause was found 26.0 ± 6.9, 20.0 ± 6.8, and 24.0 ± 7.7 mL/kg, respectively, FRC after sigh breaths and neither a sigh nor an apneic pause was significantly higher than after apneic pauses.⁽¹⁶⁾

Knowledge gap

Due to the lack of data and complexity of ventilator management trials, a clear consensus for the optimum mode of initial mechanical ventilation for neonate does not exist. The ventilation strategies used for this population vary significantly. However, HFOV is increase used as an initial ventilatory strategy especially in preterm infants including our center. Study in HFOV combined with intermittent sigh breaths in neonate is limited especially on arterial carbon dioxide level.

There were only two active but not recruiting studies which compared between HFOV with intermittent sigh breaths (HFOV-sigh) and HFOV in ClinicalTrial.gov

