(https://clinicaltrials.gov/ct2/results?cond=High+frequency+oscillatory+ventilation+with+intermittent+sigh+breath s+&term=&cntry=&state=&city=&dist=, Figure 4)^(17, 18) Both registered trials focus on preterm neonates (gestational age 24–36 weeks), sigh PIP 30 cm H₂O for 1 hour, and measured lung mechanics (electric tomography impedance) and blood oxygenation.^(17, 18) While this study fulfils this intervention by enrolled preterm and term infants (gestational age 24–41 weeks), lower sigh PIP (MAP+5, maximum sigh PIP 30 cm H₂O; usually MAP in HFOV 8–25 cm H₂O) for 2 hours, and focus on blood ventilation.

| | | | S. National Library of Medicine calTrials.gov | Find Studies ▼ A | About Studies 🕶 | Submit Studies - | Resources - Abc | out Site ▼ | PRS Login |
|-------|----------|-------------------------------------|---|------------------|--------------------------------------|-------------------------|--|----------------|-------------------|
| | | Home > | Saved Studies | | | | | Save | ed Studies (2) |
| | | | | Saved | Studies | | | | |
| Clear | Saved St | udies List | | | | | | | Download |
| | | | | | | | | | Show/Hide Columns |
| | | | | | | | | | |
| Row | Saved | Status | Study Title | | | Conditions | Intervention | ns | Locations |
| Row 1 | Saved | Status Active, not recruiting | Study Title High Frequency Oscillatory Ventilation Combined With I Lung Volume Monitored by Electric Tomography Imped | | Premature Bronchop Ventilator- | ry Distress Syndrome In | Intervention Other: HFOV comb sigh breaths | bined with • I | |

Fig. 4 Studies registered in ClinicalTrial.gov which compared "High frequency oscillatory ventilation with intermittent sigh breaths (HFOV-sigh)" with "High frequency oscillatory ventilation (HFOV)"

Objectives

Comparing the pCO_2 level after 2 hours of HFOV-sigh mode (after intervention) compared with HFOV mode (before intervention)

Conceptual framework

[figure not shown]

Fig. 5 Factors affect arterial pCO₂ level in ventilated neonates

(HFOV = High frequency oscillatory ventilation; PIP = Peak inspiratory pressure; RR = Respiratory Rate; Ti = inspiratory time)

Literature review

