- Need a new arterial puncture for samples both before and after interventions
- Moribund status
- Parents' decision not to participate

Subject withdrawal criteria

- Develop air leak syndrome during intervention
- Worsening respiratory distress with increasing HFO setting (changed Hz, MAP, delta pressure, increased FiO₂ more than 0.1, and need to suction or positive pressure ventilation via self-inflating bag or T-piece resuscitation) during study
- Hemodynamic instability and need to increase dose or add new inotrope during intervention
- Parents' decision not to participate during study

[figure not shown]
Study termination criteria

- During or after intervention within 24 hours, more than 5 neonates will develop new pulmonary air leaks (10% of 50 participants; because pulmonary air leaks occurred in HFOV 27.7% [392/1,415] in meta-analysis⁽¹⁾ so we use 10% of sample size calculation to terminate study for safety).
- The second sample after add sigh breath, more than 10 neonates have pCO₂ <35 mm Hg neonates (20% of 50 participants).

Sample size calculation

Primary outcome: Compare arterial pCO₂ level between HFOV (before) and HFOV-sigh (after)

- No previous study was compared the pCO₂ level between neonates who were on HFOV mode and HFOV + sigh mode.
- From Bonacina 2019,⁽¹⁴⁾ neonates who were on invasive PSV and PSV + sigh mode. The pCO₂ levels in PSV and PSV + sigh were 42.3 ± 3.7 mm Hg and 40.4 ± 5.0 mm Hg (Delta = 1.9 mm Hg, SD. = 4.35), respectively.

Study design was before and after intervention. The dependent outcome was pCO₂ level (continuous variable) In two dependent mean data, the calculated sample size was 42 neonates (alpha = 0.05, beta = 0.2, Delta = 1.9, SD. = 4.35), then increase 20% (if possible) for increased power. Finally, the targeted sample size was 50 neonates. We plan to recruit for one year, then preliminary analysis will do. If the result was significant differences, the study may be considered to terminate.

Operational definition

- Dependent variable = Arterial pCO₂ level
- Independent variables = Sigh breaths

Procedure

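### Should the two overlapping gestational-age subgroups (<37 and <32 weeks) be replaced by separate bands and a slope on gestational age?

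*Combined protocol and SAP*

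**What the plan says.** The Data analysis section gives two within-infant comparisons. For parametric data a "paired t-test was used to compare paired samples"; for nonparametric data "the Wilcoxon signed rank test with continuity correction was used to compare paired samples". One further sentence follows: "Subgroup analysis for gestational age less than 37 and 32 weeks". It defines no strata. It mentions no between-group contrast, regression on gestational age, confidence interval or exploratory label.

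Eligibility is wider than the named subgroups: "Preterm and term neonate (gestational age 24-41 weeks) with postnatal age less than 28 days". The Objectives and the primary outcome under Sample size calculation concern the overall before-after change in arterial pCO2. The Operational definition lists sigh breaths as the only independent variable.

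**The concern.** The two groups are nested, so their results share infants. Read literally, the sentence gives no result for 32-36 weeks and none for 37-41 weeks. Read as two cut-points (<37 against >=37, <32 against >=32), it adds the term infants, but 32-36 weeks is still pooled with one neighbour or the other. The term infants matter, because the Knowledge gap section presents the wider age range as a difference from two registered trials: "Both registered trials focus on preterm neonates (gestational age 24–36 weeks".

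Two things could go wrong. First, a pooled <37 result could hide a band with no effect. Second, if each subgroup had its own p-value, one significant and one non-significant result could be misread as an effect of maturity.

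**Working it through.** **Inputs.** From Sample size calculation: "42.3 ± 3.7 mm Hg and 40.4 ± 5.0 mm Hg (Delta = 1.9 mm Hg, SD. = 4.35"; two-sided alpha 0.05 (the sidedness that reproduces the plan's figure), power 0.80, target 50. The documents give no gestational-age mix, so every split of 50 below is assumed. The <37/<32 split 48/44 represents a mostly very preterm intake, in line with the remark that "HFOV is increase used as an initial ventilatory strategy especially in preterm infants including our center".

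**The plan's own figure.** n = (SD × (1.960 + 0.842) / delta)² = (4.35 × 2.8016 / 1.9)² = 41.14, rounded up to 42. This matches the text: "In two dependent mean data, the calculated sample size was 42 neonates". Then 42 × 1.2 = 50.4, consistent with 50. The subgroup sentence plays no part in it.

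**SD of the within-infant change.** The plan's 4.35 is (3.7 + 5.0)/2. The SD of change implied by the two condition SDs is √(3.7² + 5.0² − 2r × 3.7 × 5.0): 3.0 at r = 0.8, 4.5 at r = 0.5 and 6.2 at r = 0. Results are shown for all four values.

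**Can a band be hidden, and can it be recovered?** Take 20, 15 and 15 infants at <32, 32-36 and 37-41 weeks, with an illustrative fall of 3 mm Hg below 32 weeks and none at 32-36. The <37 mean is (20 × 3 + 15 × 0)/35 = 1.71, so the zero is masked. If sizes and means are reported, it comes back by subtraction: (35 × 1.714 − 20 × 3)/15 = 0. Medians cannot be recovered this way.

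**How often would two nested verdicts disagree under one common effect of 1.9?** Simulated normal changes in 50 infants, with a two-sided paired t-test in each nested subset:

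| <37 / <32 | SD 3.0 | SD 4.35 | SD 4.5 | SD 6.2 |
|---|---|---|---|---|
| 48 / 44 | 1% | 7% | 7% | 10% |
| 45 / 30 | 7% | 22% | 23% | 23% |
| 35 / 20 | 20% | 31% | 31% | 25% |
| 30 / 15 | 31% | 35% | 35% | 26% |

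**Is nesting or unequal size the cause?** For disjoint groups, power p comes from the noncentral t with noncentrality (1.9/SD)√n, and disagreement is p₁(1 − p₂) + p₂(1 − p₁).

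- Sizes 20 and 15 at SD 4.35: powers 0.458 and 0.351, so 0.458 × 0.649 + 0.351 × 0.542 = 0.487. Across the four SDs: 44/49/48/35%.
- Equal sizes 17 and 17 at SD 4.35: power 0.395 each, so 2 × 0.395 × 0.605 = 0.478. Across the four SDs: 43/48/47/34%.

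Equal sizes remove almost nothing, and disjoint groups disagree more often than the nested 35/20 split. The cause is low power and chance in separately tested groups.

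**False positives under no effect.** A subgroup is significant when the overall test is not in 2.1%, 4.0%, 5.5% and 6.1% of trials for the four splits. This is ordinary multiplicity.

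**What would a contrast or slope give?** Power for a 1.9 mm Hg difference between two groups (two-sample t on changes, 48 df), at SD 3.0/4.35/4.5/6.2:

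- 25 against 25: 59/33/31/18%
- 40 against 10: 42/23/22/14%
- 48 against 2: 14/9/9/7%

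The slope half-width is 2.011 × SD / (SD of gestational age × √49). With an assumed gestational-age SD of 5 to 3 weeks, it runs from 0.17 mm Hg per week (SD of change 3.0) to 0.60 (SD of change 6.2). Over the 17 weeks from 24 to 41 that is 2.9 to 10.1 mm Hg.

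**The case for a change.** The best case for a change is that it is cheap. Gestational age is already needed for eligibility. A few sentences would define the bands <32, 32-36 and 37-41 weeks, drop subgroup p-values and add a descriptive slope, and fixing the bands before analysis keeps the choice independent of the results. The Literature review also says sigh frequency rises with prematurity, so maturity is a natural descriptor.

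The description of the gap stands: 32-36 weeks is not isolated on either reading, and on the literal reading term infants are not either. The need for an amendment does not. The harm requires subgroup p-values to be set against each other, and no section plans that; even repeating the paired tests within subgroups is an inference. Asking what happens in preterm and in very preterm infants is a legitimate use of cumulative thresholds, and the <37 group matches the 24-36 week population of the two registered trials. The absence of confidence intervals is not particular to the subgroups, since the section promises none for the primary analysis either. The added slope would be a new question, with a linearity assumption that nothing in the documents supports.

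**Conclusion.** No change to the plan follows. Carried out as written, the overall result, the sample size of 50 and the safety rules are untouched, and the two subgroup summaries answer the questions they pose. Cumulative thresholds or disjoint bands is largely a matter of preference for secondary description.

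The only real hazard is one of interpretation. Separate verdicts could differ by chance in 1% to 35% of trials under the nested splits assumed here. Disjoint bands would not cure that, so a difference in verdicts should not be read as an effect of maturity, however the groups are drawn. A formal look at effect modification would gain little: power for a 1.9 mm Hg difference is at most 59%, and the slope is uncertain by at least 2.9 mm Hg over the eligible range. Precision would be worse if few term infants enrol or if recruitment ends at the one-year look.

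These figures rest on assumed gestational-age splits, normal changes and an SD of change between 3.0 and 6.2. An analyst who shows n, mean change and a 95% interval for <32, 32-36 and 37-41 weeks, labelled exploratory and without p-values, fills the gap sensibly at the reporting stage.
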